10.3.2. Secondary endpoints

The endpoints for secondary objectives of the study are defined as follows:

- Overall Response Rate (ORR) by using RECIST 1.1 (phase Ib, phase II part 2)
- Progression Free Survival (PFS) (phase Ib, Phase II part 1): time from the date of first study treatment administration to the date of first documented tumor progression or death due to any cause, whichever occurs first. If a patient has not had a PFS event at the cut-off date for analysis or at the date when a further antineoplastic therapy (other than those planned as study treatment in the protocol) is started, PFS will be censored at the date of last evaluable tumor assessment before the cut-off or start of further antineoplastic therapy.
- Overall Survival (OS):
- phase Ib and phase II part 1: time from the date of first study treatment administration to the date of death due to any cause. If a patient is not known to have died at the cut-off date for analysis, survival will be censored at the date of last contact.
- Phase II part 2: time from the date of randomization to the date of death due to any cause. If a patient is not known to have died at the cut-off date for analysis, survival will be censored at the date of last contact.
- Duration of overall Response (DoR): applies only to patients whose best overall response is CR or PR. The start date is the date of first documented response (CR or PR) and the end date is the date of first documented disease progression or death, whichever occurs first. If no progression has been observed at the cut-off date of analysis or at the date when a further antineoplastic therapy is started, DoR will be censored at the date of the last evaluable tumor assessment before the cut-off or start of further antineoplastic therapy.
- Disease control rate (DCR): proportion of patients whose best overall response is either CR, PR, or SD.
- Percentage of patients with liver metastases at baseline who have disease progression at D43 (phase II part 2)
- Safety: the assessment of safety of the combination will be based mainly on the frequency of AEs, SAEs, and on the number of laboratory values that fall outside of

predetermined ranges. Other safety data (e.g., ECG, vital signs) will be considered as appropriate.

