- For the cohort of patients without liver metastases at baseline, an adaptive sample size re-estimation is applied: based on the results obtained in phase II part 1, the hypothesis for median PFS in the combination arm (TG4001 with avelumab) is set at 4.5 months. The hypothesis for median PFS in the monotreatment arm (avelumab alone) is set at 2 months. The type I error α is set at 5% one sided, the type II error β is set at 5%.

A two-stage group sequential design will be used with logrank test and boundary for efficacy at $\alpha=0.00001$ and Conditional Power (CP) at 10% for futility.

At the interim analysis, a first test for efficacy is performed on 37 PFS events at a level of significance of 0.000001. A sample size of 50 patients is estimated at time of the Interim Analysis.

Otherwise, the following decision rules are applied based on CP using CHW (Cui, Hung and Wang) approach.

- Favorable zone: If the interim results are sufficiently favorable corresponding to a CP of more than 90%, final analysis will be performed on 74 PFS events corresponding to an estimated sample size of 80 patients.
- Promising zone: If the interim results are equivalent to a CP between 90% and 30%, the sample size will be recalculated according to the median PFS observed in the two arms with a cap of 2 times the initial number of events.

- Unfavorable zone: If the interim results are not favorable corresponding to a CP between 30% and 10%, the trial may continue up to the initial sample size of 80 patients or could be stopped.
- Futility zone: If the interim results are futile corresponding to a CP lower than 10%, the trial will be stopped for futility at the interim analysis.

[figure not shown]
Assuming uniform enrollment with 3 patients per month, an average of 136 patients are needed to observe 124 PFS events. Assuming a 5% lost to follow-up or withdrawal of consent rate, a total of 142 patients should be randomized to the 2 treatment arms in a 1:1 ratio (71 patients in each treatment arm).

[REDACTED]

[REDACTED]

[REDACTED]

[REDACTED]

- For the cohort of patients with liver metastases at baseline, [REDACTED]

[REDACTED]

[REDACTED]

[REDACTED]

[REDACTED]

TABLE OF CONTENTS

INVESTIGATORS / STUDY ADMINISTRATIVE STRUCTURE.....	2
DOCUMENT APPROVAL.....	3
SYNOPSIS.....	4
TABLE OF CONTENTS.....	17
ABBREVIATIONS / DEFINITION OF TERMS	21
1 INTRODUCTION.....	26
1.1. BACKGROUND AND INTRODUCTION	26
1.1.1. Human PapillomaVirus (HPV) and related diseases	26

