The phase II part 2 of the study is designed as a randomized, open label, controlled two arms study comparing the PFS of TG4001 in combination with avelumab vs avelumab alone. For the cohort of patients without liver metastases at baseline, due to the uncertainty on the true treatment effect and data variability, and to reduce the risk of running an underpowered study, it is considered appropriate to adopt an adaptive approach to the sample. This will offer a mechanism to adjust the sample size to updated treatment effect and variability estimates seen at a planned interim analysis (Mehta C.R. and Pocock S.J., 2011).

The hypothesis for median PFS in the combination arm (TG4001 with avelumab) is set at 4.5 months and the hypothesis for median PFS in the monotreatment arm (avelumab alone) is set at 2.0 months. Interim analysis is performed after 37 PFS events and based on the conditional power observed, 120 patients should be enrolled to reach at Final Analysis a conditional power of 90% based on 104 PFS. To stick with initial timelines and with an observed enrollment of only 2 patients per month, Final Analysis will be performed based on at least 69 PFS events reaching a conditional power higher than 75% corresponding to at least 80 randomized patients.

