With an one-sided type I error α at 5%, 76 events are needed to reach a power of 95%. This should happen after around 80 patients enrolled (40 patients per arm). Assuming 5% drop-out in each arm, 84 patients will be randomized.

[figure not shown]
Due to the uncertainty on the true treatment effect and data variability, and to reduce the risk of running an underpowered study, it is considered appropriate to adopt an adaptive approach for the sample size. This will offer a mechanism to adjust the sample size in response to treatment effect and variability estimates seen at a planned interim analysis.

The interim analysis will be conducted after 37 events which will occur approximately 16 months after the inclusion of the first patient. At that time, it is estimated to have around 50 patients enrolled. Based on the results of the interim analysis, sample size re-estimation will be performed. According to simulations on CHW (Cui, Hung and Wand) approach using EAST 6.5., the proposal is as follows:

- Start with a fixed sample size calculation based on the primary endpoint.
- Based on the interim analysis result maintain or increase the sample size in order to obtain the desired power of 90%.

Conditional power will be calculated based on the interim results. Should the conditional power be in the favorable or unfavorable range the sample size and the number of events will not be adjusted and will remain at the initial sample size. Conditional power falling into the promising zone will have a sample and events increase. The regions and their implications on sample size are detailed below:

- **Favorable:** If the interim results are sufficiently favorable corresponding to a CP of more than 90%, final analysis will be performed on 74 PFS events corresponding to an estimated sample size of 80 evaluable patients. This will occur approximately 26 months after the inclusion of the first patient.
- **Promising zone:** If the interim results are equivalent to a CP between 90% and 30%, the sample size will be recalculated according to the median PFS observed in the two arms with a cap of 2 times the initial events.
- **Unfavorable zone:** If the interim results are not favorable corresponding to a CP between 30% and 10%, the trial may continue up to the initial sample size of 80 patients or could be stopped
- **Futility:** If the interim results are futile corresponding to a CP lower than 10%, the trial will be stopped for futility at the interim analysis.

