Assuming an uniform enrollment with 3 patients per month and based on simulations, in case of sample size reassessment, an average of 124 events would be needed (corresponding to 136 patients). Assuming a 5% lost to follow-up or withdrawal of consent rate, a total of 142 patients should be randomized to the 2 treatment arms in a 1:1 ratio (71 patients in each treatment arm). Based on the aforementioned assumptions, a power of 70% is expected using an unstratified log-rank test at a 1-sided cumulative 5% level of significance. [REDACTED]

[REDACTED]

[REDACTED]

[REDACTED]

[REDACTED]

Full details of the adaptive method for sample size specified above will be given in the Statistical Analysis Plan (SAP).

Patients with liver metastases at baseline:

A sample size of [REDACTED] is planned.

[REDACTED]

[REDACTED]

[REDACTED]

[REDACTED]

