10.4. Statistical and analytical plans

10.4.1. Safety analyses

All safety analyses will be performed and summarized in the SAF.

Adverse Events

AE summaries will include all AEs starting on or after start of study treatment or that has worsened on or after start of study treatment and starting no later than 90 days after the date of last study treatment administration.

All Aes, significant Aes, Aes leading to discontinuation of study treatment (overall and by component: TG4001, avelumab), severe Aes (Grade 3 or 4) and serious Aes (SAE) will be listed and summarized by System Organ Class (SOC) and Preferred Term (PT), intensity (based on the NCI CTCAE grades, also referred as CTCAE), relationship to study treatment (TG4001 and/or avelumab).

Separate AE summaries will be presented by SOC, PT, and CTCAE grade. In the summaries presented by grade, all Aes will be pooled. Specific tables will summarize related Aes to IMP and Aes of specific interest (injection site reactions).

The frequency of CTCAE Grade 3 and 4 Aes will be summarized separately.

Written narratives will be produced for all SAEs and unexpected or other significant Aes that are judged to be of special interest because of their clinical importance.

Adverse events/SAEs occurring after signing the Informed Consent Form (ICF) but before starting study treatment, including those observed in patients screened but not included will be listed separately from those occurring after treatment start.

Fatal Events

All fatal events will be listed and summarized by System Organ Class (SOC) and Preferred Term (PT). The nature of the event leading to death should be recorded. Sudden/unexplained death will be coded as “death”.

Fatal events will be summarized by presenting the number and percentage of patients who died. Data will be presented by SOC and PT using MedDRA coding.

Fatal events occurring after signing the Informed Consent Form (ICF) but before starting study treatment in patients screened but not included will be listed separately from those occurring after treatment start.

Laboratory abnormalities

The summaries will include all laboratory assessments collected no later than 30 days after treatment discontinuation. All laboratory assessments will be listed and those collected during 30 days after study treatment discontinuation will be flagged in the listings.

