10.5.4.2. Study treatments

Exposure to TG4001 will be provided by listing and summarizing the number of injections and the duration of treatment.

Exposure to avelumab will be provided by listing and summarizing the number of infusions, the cumulated dose and the duration of treatment.

The SAF and the FAS for phase II part 2 will be used for all summaries and listings of study treatment.

The number of patients with dose omission will be presented by study treatment component, along with reasons for the dose omission.

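### Part 2 summarises adverse events only as crude frequencies although planned time on treatment differs by arm, so late-accruing events would look more common with TG4001 even at equal toxicity

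*Combined protocol and SAP*

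**What the plan says.** Safety profile is a phase II secondary objective (section 2.2). Section 10.3.2 states that "the assessment of safety of the combination will be based mainly on the frequency of AEs, SAEs", together with the number of laboratory values outside preset ranges. Section 10.4.1 summarises AEs by system organ class, preferred term, grade and relationship, and adds that "The frequency of CTCAE Grade 3 and 4 Aes will be summarized separately". Laboratory shift tables use the worst post-baseline value.

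The AE summaries reach to 90 days after the last dose and the laboratory summaries to 30 days after discontinuation (10.4.1). Section 9.2 collects every AE for only the first 30 of those days; from then to day 90 it collects SAEs and treatment-related non-serious AEs.

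Part 2 patients are treated until progression, toxicity, death or withdrawal, for up to 2 years (3.1.1), with some continuation allowed after a first radiological progression (6.2.2). On planned PFS, section 3.2 says "The hypothesis for median PFS in the combination arm (TG4001 with avelumab) is set at 4.5 months". For avelumab alone the corresponding figure is 2.0 months.

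Exposure is reported on its own in 10.5.4.2: "Exposure to avelumab will be provided by listing and summarizing the number of infusions, the cumulated dose and the duration of treatment". It is not used as a denominator or time axis for AEs. The text available contains no time-to-first-event analysis, rate per patient-time or common-window table.

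**The concern.** Under the design hypothesis the combination arm stays on treatment, and under AE collection, for longer. The proportion of patients with at least one event, the number of events and the worst laboratory grade can only rise with time at risk. The better TG4001 works, the worse its columns will look beside avelumab alone.

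This matters most for delayed immune-related events. Appendix V gives median onset on avelumab monotherapy of 2.5 months for pneumonitis, 3.3 for hepatitis, 2.0 for colitis, 2.8 for thyroid disorders and 3.3 for adrenal insufficiency. All are at or beyond the planned 2.0-month control median, so many control patients would have stopped before the typical onset. Part 2 is the only randomised evidence on what TG4001 adds, and the IDMC reviews its safety data (3.1.3).

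**Working it through.** **Check of the PFS inputs.** HR = 2.0/4.5 = 0.444. With one-sided alpha 5% and power 95%, Freedman's formula gives (1.645 + 1.645)² × (1.444/0.556)² = 10.82 × 6.76 = 73.2, so 74 events. Section 10.2 states that "76 events are needed to reach a power of 95" per cent, and uses 74 for the final analysis. The two medians are therefore the real planning values. No sample-size figure is disputed here.

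**Model.** PFS is exponential with μ = ln 2/median: 0.154 per month (combination) and 0.347 (avelumab alone). Treatment time T = min(PFS, 24 months). The AE window is T + w, with w = 30 or 90 days (0.99 or 2.96 months). The AE rate λ is an assumption, because the documents give none for this trial. It is constant and identical in both arms, so the true difference is zero.

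**Mean time at risk.** E[T] = (1 − e^(−24μ))/μ = 6.33 v 2.88 months, ratio 2.19. With 30 days added: 7.32 v 3.87, ratio 1.89. With 90 days added: 9.29 v 5.84, ratio 1.59. Expected event counts scale with these ratios.

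**Crude percentage with an event.** P = 1 − e^(−λw) × E[e^(−λT)], where E[e^(−λT)] = μ/(μ+λ) × (1 − e^(−24(μ+λ))) + e^(−24(μ+λ)). Example for λ = 0.10 and w = 90 days: e^(−λw) = 0.744; E = 0.607 and 0.776; P = 1 − 0.744 × 0.607 = 54.8% and 1 − 0.744 × 0.776 = 42.3%.

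| Window after last dose | λ per month | Combination | Avelumab alone | Gap (points) |
|---|---|---|---|---|
| 90 days | 0.01 | 8.7% | 5.6% | 3.1 |
| 90 days | 0.05 | 34.7% | 24.6% | 10.1 |
| 90 days | 0.10 | 54.8% | 42.3% | 12.6 |
| 90 days | 0.20 | 75.9% | 64.9% | 11.0 |
| 90 days | 1.0 | 99.3% | 98.7% | 0.6 |
| 30 days | 0.05 | 28.0% | 16.8% | 11.2 |
| 30 days | 0.10 | 45.0% | 29.7% | 15.3 |

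By section 9.2, the 90-day rows fit SAEs and related AEs. The 30-day rows fit unrelated non-serious AEs and laboratory values.

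**Smaller effect.** With HR 0.60 (median 2.0/0.60 = 3.3 months), the gaps at 0.05 and 0.10 are 6.4 and 9.1 points (30 days) or 5.8 and 7.5 points (90 days). This case is relevant because section 3.2 reports 104 events for 90% conditional power after an interim at 37. Assuming equal weights (37 of 74) and the current trend, z₁ × (1 + √(67/37)) = 1.282 + 1.645/√0.5 = 3.608. So z₁ = 1.54, and ln HR = −1.54/√(37/4) = −0.506, which gives HR of about 0.60.

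**Early events.** If risk is confined to the first month of treatment, the crude ratio is only 1.09; for the first two weeks it is 1.05.

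**Exposure-adjusted rates on early events.** If the same proportion in each arm has the event near the start, first events per patient-month have a ratio close to the inverse ratio of time at risk: 3.87/7.32 = 0.53 (30 days) or 5.84/9.29 = 0.63 (90 days). Events at about two weeks with 40% risk move the latter to 0.64. TG4001 would look safer although true risk is equal.

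**The case against.** **No between-arm safety comparison is specified.** A reader might infer that the plan formally compares safety between arms. It does not. The quoted sentence assesses the combination, exploratory procedures serve only to flag findings (10.4.1), and the synopsis says safety data will not be analysed statistically, although that line stands ahead of its part 2 text. This stands. It changes how the distortion enters, not whether it does: the descriptive columns are the whole planned safety evidence, and they will be read side by side.

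**The added toxicity of TG4001 is not wholly unreadable.** A reader might infer that the planned tables say nothing about it. Section 10.4.1 includes tables by relationship to each product, discontinuations by component and injection site reactions, and treatment duration is tabulated. These help in part. Attribution is by the investigator in an open-label trial, and a separate duration table does not correct an AE percentage.

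**The median ratio is not the inflation factor.** Reading 4.5/2.0 = 2.25 as the excess in AEs is unsupported. The follow-up window cuts the time-at-risk ratio to 1.59 or 1.89, very common events reach a ceiling, and many reactions come early. Section 1.2.2.3 places 197 of 215 infusion-related reactions (149 + 48, or 92%) at infusion 1 or 2, and TG4001 is given most densely in the first weeks. All of this stands and limits the point to events that accrue over time.

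**Further detail may lie elsewhere.** The protocol refers to a statistical analysis plan for some details. Its safety section is not in the text available, so an adjustment there cannot be excluded.

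**Conclusion.** The point holds in limited form. Crude frequencies will overstate the relative toxicity of the combination arm for low- to mid-frequency events that accrue over time, if TG4001 prolongs PFS. At an equal constant rate of 0.05 to 0.10 per month, the spurious gap is about 10 to 13 points (90-day window) or 11 to 15 points (30-day window) under the planned medians, and about 6 to 9 points at HR 0.60. It vanishes if PFS is equal, and it is small for early or near-universal events.

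The sizes rest on an assumed AE rate, exponential PFS, treatment that stops at progression, and the cohort without liver metastases. The safety population also includes patients with liver metastases, to whom these medians do not apply. Treatment beyond a first progression changes exposure in both arms by an unknown amount.

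**What to change.** In section 10.4.1, for part 2, add by arm:

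1. Cumulative incidence or time to first event for grade 3 or higher AEs, SAEs, related AEs and immune-related AEs. Censor at the end of the AE window that applies to each category under section 9.2, and treat death as a competing event.
2. AE percentages within one common early window, for example up to the first scheduled scan on Day 43.
3. A statement that between-arm safety is read from these displays beside the crude percentages.

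State the time origin, because avelumab-alone patients take their first dose a week after randomisation. Fix the list of immune-related terms in advance, since the only AEs of specific interest that 10.4.1 names are injection site reactions.

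Exposure-adjusted rates may be shown as a supplement. They should not be the sole basis, because they assume a constant hazard and give a ratio of about 0.53 to 0.64 for early events with equal true risk.

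The cost is a few extra tables and figures and one term list. Dosing dates and AE onset dates are already collected, and there is no added burden on patients or sites.

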10.3.3. Exploratory endpoints (phase Ib and II)

- To assess the following blood-based parameters and their impact on clinical outcomes (baseline and on-treatment sampling):
 - Memory and naïve T cells, regulatory T cells, CD8+ T cells, B cells, NK cells, and activation thereof
 - TG4001 and HPV-16-specific and tumor specific humoral and cellular immune responses
 - Immune related soluble factors and cytokines
- To assess tumor-based proteins and RNAs expression with potential prognostic and/or predictive value on efficacy outcomes including PD-L1 expression as well as new biomarkers identified by transcriptomic analysis (biopsies at baseline, on-treatment and at progressive disease)
- To assess the level of tumor infiltrating lymphocytes (TILs) and phenotypic characteristics thereof (biopsies at baseline, on-treatment and at progressive disease)
- To assess tumor mutation load and describe its impact on clinical outcomes (biopsies at baseline, on-treatment and at progressive disease)
- To assess viral clearance

10.4. Statistical and analytical plans

10.4.1. Safety analyses

All safety analyses will be performed and summarized in the SAF.

Adverse Events

AE summaries will include all AEs starting on or after start of study treatment or that has worsened on or after start of study treatment and starting no later than 90 days after the date of last study treatment administration.

All Aes, significant Aes, Aes leading to discontinuation of study treatment (overall and by component: TG4001, avelumab), severe Aes (Grade 3 or 4) and serious Aes (SAE) will be listed and summarized by System Organ Class (SOC) and Preferred Term (PT), intensity (based on the NCI CTCAE grades, also referred as CTCAE), relationship to study treatment (TG4001 and/or avelumab).

Separate AE summaries will be presented by SOC, PT, and CTCAE grade. In the summaries presented by grade, all Aes will be pooled. Specific tables will summarize related Aes to IMP and Aes of specific interest (injection site reactions).

The frequency of CTCAE Grade 3 and 4 Aes will be summarized separately.

Written narratives will be produced for all SAEs and unexpected or other significant Aes that are judged to be of special interest because of their clinical importance.

Adverse events/SAEs occurring after signing the Informed Consent Form (ICF) but before starting study treatment, including those observed in patients screened but not included will be listed separately from those occurring after treatment start.

Fatal Events

All fatal events will be listed and summarized by System Organ Class (SOC) and Preferred Term (PT). The nature of the event leading to death should be recorded. Sudden/unexplained death will be coded as “death”.

Fatal events will be summarized by presenting the number and percentage of patients who died. Data will be presented by SOC and PT using MedDRA coding.

Fatal events occurring after signing the Informed Consent Form (ICF) but before starting study treatment in patients screened but not included will be listed separately from those occurring after treatment start.

Laboratory abnormalities

The summaries will include all laboratory assessments collected no later than 30 days after treatment discontinuation. All laboratory assessments will be listed and those collected during 30 days after study treatment discontinuation will be flagged in the listings.

All laboratory values will be converted into SI units and will have a severity grade calculated using appropriate common terminology criteria for Aes (NCI CTCAE, version 4.03 for phase Ib and phase II part 1, version 5.0 for phase II part 2). A listing of laboratory values will be provided by laboratory parameter and patient. A separate listing will display notable laboratory abnormalities (i.e., newly occurring CTCAE Grade 3 or 4 laboratory toxicities). The frequency of these notable laboratory abnormalities will be displayed by parameter. The shift tables using CTCAE grades to compare baseline to the worst post-baseline value will be produced for all relevant safety measures as described in the statistical analysis plan. Note that for parameters with two directions abnormalities (hypo/hyper), two tables will be presented. Laboratory abnormalities occurring after signing the Informed Consent Form (ICF) but before starting study treatment, including those observed in patients screened but not included will be listed separately from those occurring after treatment start.

Other safety data

Other safety data (e.g., vital signs, electrocardiogram) will be listed, notable values will be flagged, and any other information collected will be listed as appropriate. Any statistical procedures performed in order to explore the data will be used only to highlight any interesting comparisons that may warrant further consideration.

